2.2 SAMPLE SIZE DETERMINATION

The sample size was estimated on the basis of data from Study WA25046 (ORATORIO).

A two-group test of equal exponential survival is used to determine the sample size for the composite 12-week CDP of EDSS and 9-HPT. With a sample size of 1000 patients (of which at least 350 patients are expected in the MRI-active population), a double-blind treatment phase of 144 weeks, an annual dropout rate of 10%, and a randomization ratio of 1:1, it is expected that approximately 340 events will be observed in all randomized patients (placebo progression rate: 40%), which will provide approximately 80% power to detect a hazard ratio (HR) of 0.70 at a type I error rate of 0.0146 and approximately 75.5% power to detect a HR of 0.75 at a type I error rate of 0.05. Likewise, it is expected that approximately 122 events will be observed in the MRI-active subgroup (placebo progression rate: 44%), which will provide approximately 78% power to detect a HR of 0.60 at a type I error rate of 0.04.

Operating characteristics (power and expected total number of events) for true underlying HR values of 0.60, 0.70, and 0.75 are provided in [Table 4](#) for all randomized patients and the MRI-active subgroup.

Table 4 Operating Characteristics for Possible True Underlying Hazard Ratio Values

	MRI-Active Subgroup	All Patients Randomized	All Patients Randomized
Expected number of events	122	340	340
Expected proportion of placebo patients with composite events at Week 120	44%	40%	40%
2-sided alpha for the log-rank test	0.04	0.0146	0.05
Power	78%	80%	75.5%
Detectable hazard ratio	0.60	0.70	0.75

MRI = magnetic resonance imaging.

Note: Operating characteristics are based on the following assumptions: event times are exponentially distributed, and patients are followed for 144 weeks.

It should be noted that the type I error rate to be used for the testing in all randomized patients will be adjusted depending on the proportion of events in the MRI-active subgroup at the primary analysis.

3. **ANALYSIS SETS**

The analysis sets are defined in [Table 5](#).

Table 5 Participant Analysis Sets

Participant Analysis Set	Description
Full analysis set	All randomized participants; participants will be included in the analyses according to the treatment to which they were assigned.

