2. The primary analysis is performed under the independent censoring assumption. However, this assumption may not be plausible. A similar tipping point analysis as the one described in 1. will be conducted for patients who experience censoring because of the following:
 - Initiation of another MS DMT or commercial ocrelizumab
 - Withdrawal from study (missing data)

Additionally, if at least 10% of the patients randomized to the ocrelizumab arm experience censoring because of the above, a sensitivity analysis may be performed, where it will be attempted to predict the onset of composite 12-week CDP event times for these patients using the observed profile of patients randomized to the placebo arm. The proposed approach appears conservative yet plausible for the study drug. It assumes no treatment effect after the censoring. In the placebo arm, this is compatible with a missing at random (MAR) assumption whereas in the active drug arm, the imputation is under a missing not at random (MNAR) assumption. The proposed sensitivity analysis is based on the multiple imputation approach in [Atkinson et al. 2019](#). Specifically, the following steps will be applied:

- a) Fit a Weibull model with hazard function $\alpha \cdot \text{time}^{\alpha-1} \exp\{\beta_0 + \beta_1 X_i\}$ to time to onset of composite 12-week CDP in patients randomized to the placebo arm. Here, α , β_0 , β_1 are unconstrained parameters to be estimated, time is time from randomization, X_i is a vector containing the baseline EDSS and 9-HPT values for patient i .

- b) Simulate 100 sets of $\{\alpha, \beta_0, \beta_1\}$, from the estimated asymptotic normal distribution of the maximum likelihood estimator of these parameters.
- c) Let W_i be the time from randomization for patient i at the time of withdrawal from the study or initiation of another MS DMT or commercial ocrelizumab. Let F_i be the time from randomization for patient i at the clinical cut-off date or at week 144, whichever is earlier. For each set of simulated parameter values, generate onset of composite 12-week CDP event times for patients who have not had composite 12-week CDP up to and including W_i , and where $W_i < F_i$. This will result in 100 complete analysis data sets, i.e., where composite 12-week CDP events times are either available or are censored at F_i . In order to simulate composite 12-week CDP events time O_i for patient i , the following formula will be used:

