$$O_i = \{W_i^\alpha - \log(U_i) \exp(-\beta_0 - \beta_1 X_i)^\alpha\}^{\frac{1}{\alpha}}$$

Here, U_i is generated from a standard uniform distribution. If $O_i > F_i$, the onset time of composite 12-week CDP is recorded as censored at F_i in the analysis data set, otherwise it is set to O_i .

- d) For each of the 100 complete analysis data sets, estimate the log HR and its associated standard error with the Cox model used for the primary analysis. Then, use Rubin's rules to combine the estimates from the 100 complete data sets, as described in sensitivity analysis 1, to obtain an overall estimate of the treatment effect on the HR scale and associated 95% Wald interval.

4.2.4 **Supplementary Analyses for Co-Primary Estimand 1**

1. The primary analysis will be repeated after excluding patients who meet the exclusion criteria/do not meet the inclusion criteria listed below at baseline.

Inclusion criteria:

- Diagnosis of PPMS in accordance with the McDonald criteria ([Thompson et al. 2017](#))
- Age 18–65 years at time of signing Informed Consent Form
- EDSS score at screening and baseline ≥ 3.0 to 8.0, inclusive
- Disease duration from the onset of MS symptoms relative to randomization date:
 - Less than 20 years in patients with an EDSS score at screening 7.0–8.0
 - Less than 15 years in patients with an EDSS score at screening 5.5–6.5
 - Less than 10 years in patients with an EDSS score at screening ≤ 5.0
- Documented history or presence at screening of at least one of the following laboratory findings in a CSF specimen (source documentation of laboratory results and method must be verified)
 - Elevated IgG index

- One or more IgG oligoclonal bands detected by isoelectric focusing
- Screening and baseline 9-HPT completed in > 25 seconds (average of the two hands)
- Ability to complete the 9-HPT within 240 seconds with each hand at screening and baseline
- Neurological stability for ≥ 30 days prior to baseline

Exclusion criteria:

- History of relapsing-remitting or secondary progressive MS at screening
- Patients requiring symptomatic treatment of MS (e.g., fampridine) and/or physiotherapy who are not on a stable regimen. Patients must not initiate symptomatic treatment of MS or physiotherapy within 4 weeks of randomization
- Known presence of other neurologic disorders that could interfere with the diagnosis of MS or assessments of efficacy and/or safety during the study

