4.2.6 Sensitivity Analyses for Co-Primary Estimand 2

The sensitivity analysis for co-primary estimand 2 will be similar to the sensitivity analysis for co-primary estimand 1 except the population will be patients with PPMS, including patients later in their disease course, as defined by the study inclusion and exclusion criteria (see Sections 4.1.1 and 4.1.2 of the protocol).

4.2.7 Supplementary Analyses for Co-Primary Estimand 2

The supplementary analyses for co-primary estimand 2 will be similar to the supplementary analyses for co-primary estimand 1 except the population will be patients with PPMS, including patients later in their disease course, as defined by the study inclusion and exclusion criteria (see Sections 4.1.1 and 4.1.2 of the protocol).

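### The placebo-based imputation fits one Weibull model and simulates from another, so imputed event times do not follow the fitted placebo hazard unless alpha = 1, and they depend on an unstated time unit

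*SAP*

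**What the plan says.** SAP 4.2.3, item 2, concerns patients censored because they started another MS DMT or commercial ocrelizumab, or withdrew from the study. A tipping-point analysis of them is planned. In addition, "if at least 10% of the patients randomized to the ocrelizumab arm experience censoring because of the above, a sensitivity analysis may be performed". SAP 4.2.6 extends this to the other population: "The sensitivity analysis for co-primary estimand 2 will be similar to the sensitivity analysis for co-primary estimand 1".

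The optional analysis has these steps:

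- (a) For the placebo arm: "Fit a Weibull model with hazard function $\alpha \cdot \text{time}^{\alpha-1} \exp\{\beta_0 + \beta_1 X_i\}$ to time to onset of composite 12-week CDP". Alpha, b0 and b1 are all estimated freely. X holds baseline EDSS and 9-HPT. On the time scale the SAP says only that "time is time from randomization".
- (b) Draw 100 sets of the same three parameters from their estimated asymptotic normal distribution.
- (c) For a patient event-free at W, generate the event time as the 1/alpha power of W^alpha minus this term: "\log(U_i) \exp(-\beta_0 - \beta_1 X_i)^\alpha".
- (d) Refit the Cox model in each data set and combine with Rubin's rules.

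The SAP justifies the approach in these words: "The proposed approach appears conservative yet plausible for the study drug. It assumes no treatment effect after the censoring".

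**The concern.** The parameters go straight from (a) to (c) with no conversion, so (c) must invert the hazard in (a). It does not, because of the extra exponent alpha.

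The analysis is meant to show what happens if censored patients progress at the placebo rate from then on. As written, neither arm is imputed at the fitted placebo rate, so the missing-at-random description fails even for placebo. If alpha is above 1, the stress test is milder than described and makes the result look more robust than it is. If alpha is below 1, it is harsher. These directions hold when b0+b1X is negative, as in every setting below. Two programmers who follow the SAP exactly, one in days and one in years, would report different hazard ratios from the same data.

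**Working it through.** **Inputs from the SAP**

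- Hazard and simulation formula: 4.2.3, item 2(a) and (c).
- Placebo event proportion at Week 120: 44% MRI-active, 40% all randomized; hazard ratios 0.60 and 0.70 (2.2, Table 4).
- Dropout: "an annual dropout rate of 10" percent (2.2).
- Horizon: Week 144, the latest allowed by step (c).

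**Assumed, because the SAP does not give them:** alpha from 0.8 to 1.4; time in days, weeks or years; censoring at Week 48 in the probability example. The SAP reports no numerical result for this analysis, so the formula itself is what is checked.

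**Algebra.** Write eta = b0 + b1X.

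1. The step (a) hazard `alpha * t^(alpha-1) * exp(eta)` has cumulative hazard `t^alpha * exp(eta)`.
2. Given no event by W, `S(O|W) = exp{-(O^alpha - W^alpha) exp(eta)}`. Setting this equal to U gives `O = {W^alpha - log(U) exp(-eta)}^(1/alpha)`.
3. Step (c) has `exp(-alpha*eta)` in place of `exp(-eta)`. That inverts `alpha * t^(alpha-1) * exp(alpha*eta)`, which is the fitted hazard times `exp{(alpha-1)eta}`. The factor is 1 only if alpha = 1 or, trivially, eta = 0.

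**Time unit.** Multiply all times by c. The fitted eta becomes `eta - alpha*log(c)`. In the correct formula both terms scale by c^alpha, so O simply rescales. In step (c) the second term scales by c^(alpha^2) while W^alpha scales by c^alpha, so the imputed times change.

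**Probability of an imputed event, Week 48 to Week 144.** Set `exp(eta) = -ln(1-p)/120^alpha`. Worked case, MRI-active, alpha 1.2, weeks:

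- -ln(0.56) = 0.580, so eta = ln(0.580) - 1.2*ln(120) = -6.29.
- (144^1.2 - 48^1.2) * exp(eta) = 0.529, so the fitted model gives 1 - exp(-0.529) = 0.41.
- Factor exp(0.2 * -6.29) = 0.284, and 0.529 * 0.284 = 0.150, so as written the result is 1 - exp(-0.150) = 0.14.

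| Population | alpha | Fitted model (any unit) | As written: days | weeks | years |
|---|---|---|---|---|---|
| MRI-active | 0.8 | 0.32 | 0.72 | 0.61 | 0.39 |
| MRI-active | 1.1 | 0.39 | 0.20 | 0.24 | 0.35 |
| MRI-active | 1.2 | 0.41 | 0.09 | 0.14 | 0.32 |
| All randomized | 1.2 | 0.37 | 0.08 | 0.12 | 0.28 |

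A fit to simulated data behaves the same way. One set of 500 placebo patients (203 events) gave an estimated alpha of 1.345 in every unit. From Week 72 to Week 144 the fitted model gave 32.1% in every unit; the SAP formula gave 1.3% (days), 3.3% (weeks) and 18.7% (years).

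**Effect on the hazard ratio.** The simulation used 1,000,000 patients per arm, exponential dropout of 10% a year (all treated as this type of censoring), cut-off at Week 144 and an unstratified Cox model. The Monte Carlo SE of each hazard ratio is about 0.002, and the two imputations share random draws.

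| Population (true HR) | alpha, unit | No imputation | Correct imputation | As written | Error |
|---|---|---|---|---|---|
| MRI-active (0.60) | 1.1, weeks | 0.601 | 0.648 | 0.635 | -0.013 |
| MRI-active (0.60) | 1.2, weeks | 0.601 | 0.652 | 0.626 | -0.026 |
| MRI-active (0.60) | 1.2, years | 0.599 | 0.648 | 0.640 | -0.008 |
| MRI-active (0.60) | 1.4, weeks | 0.602 | 0.653 | 0.617 | -0.036 |
| MRI-active (0.60) | 0.8, weeks | 0.599 | 0.639 | 0.663 | +0.024 |
| All randomized (0.70) | 1.2, weeks | 0.700 | 0.737 | 0.717 | -0.020 |
| All randomized (0.70) | 0.8, weeks | 0.699 | 0.730 | 0.751 | +0.021 |

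Across all 30 settings run, the error is 0.003 to 0.04 in absolute size, and the as-written hazard ratio always lies nearer 1 than the one without imputation. For MRI-active at alpha 1.2 in weeks, the formula delivers about half the intended shift: (0.626-0.601)/(0.652-0.601). At alpha 0.8 in weeks it delivers 1.6 times: (0.663-0.599)/(0.639-0.599).

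**Could the 10% trigger be met?** In the simulation, 20-21% of the ocrelizumab arm is censored event-free before Week 144. That is an upper figure, because it counts all dropout as this type of censoring.

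**The case against.** The strongest reply is that little rests on this analysis. It is conditional on the 10% trigger and optional even then. It carries no alpha and no success criterion. The tipping-point analysis of the same censored patients does not use the formula, and neither does the treatment-policy estimand in 4.2.4. All of this is true and limits the weight of the point.

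The hazard-ratio errors above are also on the high side. Some withdrawals are imputed as events rather than censored (lack of efficacy, or an initial progression at the last assessment), and patients off treatment without another therapy stay in follow-up. A rerun with about 10% of the ocrelizumab arm censored roughly halves the errors. For alpha 0.8 to 1.2 across the units they are 0.002-0.019 (MRI-active) and 0.002-0.016 (all randomized); at alpha 1.2 in weeks, 0.013 and 0.010. Sampling error is larger: with 122 events SE(log HR) is about 2/sqrt(122) = 0.18, so even the 0.652 versus 0.626 contrast is ln(0.652/0.626)/0.18, about 0.2 SE.

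The only event-time shape the SAP assumes is exponential, where the error is zero. But step (a) estimates alpha freely, so the plan does not rely on that shape here. Finally, the exponent was read from a converted PDF and could be a conversion fault, so it should be checked on the page. None of this reconciles (a) with (c) as they stand.

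**Conclusion.** The concern holds. Step (c) does not simulate from the model fitted in step (a) unless alpha is 1, and its output depends on a time unit that the SAP leaves open. The unit problem follows from the same mismatch and is not a second fault.

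The size rests on assumed shapes and units, a common eta for all patients and an unstratified Cox model; variation between patients through their covariates was not quantified. The algebra is certain for the text as read. The damage is confined to one optional sensitivity analysis for each co-primary estimand; the primary test and the alpha split are untouched. It should still be corrected, because the analysis would not do what the SAP says it does, and a programmer who silently repaired it would be departing from the plan.

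**What to change.** Check the exponent in step (c) against the original PDF. If it is there, do one of the following:

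- replace step (c) with `O_i = {W_i^alpha - log(U_i) * exp(-b0 - b1*X_i)}^(1/alpha)`; or
- keep step (c) and restate the step (a) hazard as `alpha * t^(alpha-1) * exp{alpha(b0 + b1*X_i)}`.

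Either change makes the imputed times follow the fitted placebo model and removes the dependence on the time unit. The correction carries through to 4.2.6 by reference. The cost is a one-line SAP correction before unblinding, with no change to data or design.

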4.2.8 Subgroup Analyses for Primary Endpoint

Refer to Section 4.4 and Section 4.6.8 for the subgroup analyses for the primary endpoint.

4.3 SECONDARY ENDPOINTS ANALYSES

Hypothesis tests for the secondary estimands are described in Section 2.1 .

If only one of the co-primary estimands is positive, the secondary endpoints will be tested for all randomized patients and the MRI-active subgroup but the p-value will not be confirmatory.

If both co-primary estimands are statistically significant, then the secondary endpoints will be tested with $\alpha=0.05$ in a hierarchical gatekeeping procedure for all randomized patients in the order listed below, and as exploratory in the MRI-active subgroup:

- Time to 12-week CDP in 9-HPT
- Time to 12-week CDP in EDSS
- Time to 24-week CDP in 9-HPT
- Time to 24-week CDP in EDSS
- Annual rate of change from baseline in radius of total volume of T2 lesions

- Annual rate of percent change from Week 24 in total brain volume

All attributes for the secondary estimands are provided in [Table 1](#). Further details on the estimands attributes and estimation methods (i.e., estimators) are provided below.

4.3.1 Estimands for Time to Event Endpoints

All secondary estimands which focus on the analysis of time to event endpoints have the same estimand attributes (except for Endpoint attribute) and estimation method as for the co-primary estimand 2 (Section [4.2.5](#)).

The time to 12-week CDP in 9-HPT and time to 12-week CDP in EDSS are the individual components of the composite 12-week CDP as defined in Section [4.2.1](#).

The time to 24-week CDP in 9-HPT and time to 24-week CDP in EDSS will be defined over a 24-week confirmation window (≥ 161 days) for the disability progression.

4.3.2 Estimand for Annual Rate of Change from baseline in radius of total volume of T2 lesions

Estimand: The estimand is the mean difference in annual rate of change from baseline in radius of total volume of T2 lesions between the experimental and control arms in patients with PPMS, including patients later in their disease course, where no treatment discontinuation nor initiation of another MS DMT or commercial ocrelizumab can occur.

Estimator: A random coefficient regression model (RCRM) will be used to quantify the mean difference in annual rate of change from baseline in radius of total volume of T2 lesions between the experimental and control arms. The mean structure of the model is as follows:

$$E[Y_{ij} | time_{ij}, T_i, X_i] = time_{ij}(\beta_0 + \alpha X_i + \beta_1 T_i + u_i),$$

where Y_{ij} represents change in the cube root of total volume of T2 lesions from baseline at visit j for patient i , $time_{ij}$ is the time from baseline in years at visit j for patient i , T_i is an indicator such that $T_i = 1$ if patient i was randomized to the ocrelizumab arm and $T_i = 0$ otherwise, X_i is a vector containing the cube root of the baseline total volume of T2 lesions and randomization stratification factors for patient i , α is a vector of regression coefficients for X_i , β_0 is the adjusted mean of the annualized rate of change in radius of total volume of T2 lesions for the placebo arm, β_1 is the adjusted mean difference in the annualized rate of change in radius of total volume of T2 lesions between the experimental and control arms, and u_i is a subject-specific random effect that follows a mean zero normal distribution with unknown common variance for all patients. Only scheduled visits will be included in the analysis. The statistical significance of the estimated mean difference will be calculated by using the Wald test, where the standard error is estimated using the robust sandwich variance estimator.

In order to estimate the aforementioned estimand, the following intercurrent event handling strategies will be applied:

Withdrawal from treatment and no initiation of another MS DMT or commercial ocrelizumab: All data after treatment discontinuation will be treated as missing following the hypothetical strategy.

Withdrawal from treatment and initiation of another MS DMT or commercial ocrelizumab: All data after treatment discontinuation will be treated as missing following the hypothetical strategy.

Sample Statistical Analysis System code can be found below (Statistical Analysis System code is regarded as “draft” until fully validated at the analysis stage):

```
PROC MIXED DATA=dataset empirical;  
CLASS USUBJID ARMCD StratificationFactors;  
MODEL AVAL_N= ARMCD Baseline StratificationFactors / solution cl;  
RANDOM intercept / subject=USUBJID type=un;  
run;
```

where AVAL_N is the change from baseline in the cube root of the total volume of T2 lesions divided by time at each scheduled visit, and Baseline is the cube root of the total volume of T2 lesions at baseline.

4.3.3 Estimand for Annual Rate of Percent Change from Week 24 in Total Brain Volume

Estimand: The estimand is the mean difference in annual rate of percent change from Week 24 in total brain volume between the experimental and control arms in patients with PPMS, including patients later in their disease course, where no treatment discontinuation nor initiation of another MS DMT or commercial ocrelizumab can occur.

Estimator: An RCRM will be used to quantify the mean difference in annual rate of percent change from Week 24 in total brain volume between the experimental and control arms. The mean structure of the model is as follows:

$$E[Y_{ij}|time_{ij}, T_i, X_i] = time_{ij}(\beta_0 + \alpha X_i + \beta_1 T_i + u_i),$$

where Y_{ij} represents percentage change in total brain volume from Week 24 at visit j for patient i , $time_{ij}$ is the time from Week 24 in years at visit j for patient i , T_i is an indicator such that $T_i = 1$ if patient i was randomized to the ocrelizumab arm and $T_i = 0$ otherwise, X_i is a vector containing the cube root of the Week 24 total brain volume and randomization stratification factors for patient i , α is a vector of regression coefficients for X_i , β_0 is the adjusted mean of the annualized rate of percentage change in total brain volume for the placebo arm, β_1 is the adjusted mean difference in the annualized rate of Ocrelizumab—F. Hoffmann-La Roche Ltd
Statistical Analysis Plan WA40404

percentage change in total brain volume between the experimental and control arms, and u_i is a subject-specific random effect that follows a mean zero normal distribution with unknown common variance for all patients. Only scheduled visits will be included in the analysis.

The statistical significance of the estimated mean difference will be calculated by using the Wald test, where the standard error is estimated using the robust sandwich variance estimator.

In order to estimate the aforementioned estimand, the following intercurrent event handling strategies will be applied:

Withdrawal from treatment and no initiation of another MS DMT or commercial ocrelizumab: All data after treatment discontinuation will be treated as missing following the hypothetical strategy.

Withdrawal from treatment and initiation of another MS DMT or commercial ocrelizumab: All data after treatment discontinuation will be treated as missing following the hypothetical strategy.

Sample Statistical Analysis System code can be found below (Statistical Analysis System code is regarded as “draft” until fully validated at the analysis stage):

```
PROC MIXED DATA_ = dataset empirical;  
CLASS USUBJID ARMCD StratificationFactors;  
MODEL AVAL_N = ARMCD Week24 StratificationFactors / solution cl;  
RANDOM intercept / subject=USUBJID type=un;  
run;
```

where AVAL_N is the percent change from Week 24 in total brain volume divided by time at each scheduled visit, and Week24 is the cube root of the Week 24 total brain volume.

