4.5.10 Mandatory and Optional MRI Sequences

MRI will be used to monitor CNS lesions in patients with MS and potentially other pathophysiology, such as inflammation and neurodegeneration. Mandatory MRI scans (formally known as 'brain MRI') will be obtained in all patients at study visits as indicated in [Appendix 1](#), [Appendix 2](#), [Appendix 3](#), and [Appendix 4](#).

During the screening phase, two mandatory MRI scans (performed at least 6 weeks apart, but not more than 24 weeks apart) or one MRI with the mandatory sequences that can be compared with a historical MRI acquired in the previous 1 year will be performed to assess the patient's MRI activity level. MRI activity is defined as the presence of any T1 Gd+ lesion(s) and/or new and/or enlarging T2 lesion(s) during the screening period (see also Section 3.1). If the presence of new or enlarging lesions is ascertained, the patient will be stratified to the MRI-active subgroup. The MRI performed closer to randomization (i.e., either the second MRI scan at screening or the [only] screening MRI scan in the case where a historical scan was used for the assessment of MRI activity) will be considered as baseline MRI for the study analyses and will be captured under the baseline visit in the eCRF. Note that this baseline scan should be obtained maximum 6 weeks before but at least 10 days prior to performing the baseline visit to allow time for the centralized reading center to assess its quality and for potential re-scans if needed.

Postbaseline, the mandatory MRI scans will be obtained in all patients at Weeks 24, 48, and 72. From Week 72 onward, MRI scans will be performed every 48 weeks (i.e., at Week 120, 168, etc.). In addition, mandatory MRI scans will be obtained in patients who withdraw from study treatment (at withdrawal visit) if one was not performed during the prior 4 weeks. Mandatory MRI scans should occur within a window of ± 4 weeks of the scheduled visit, as per the schedules of activities (see [Appendix 1](#), [Appendix 2](#), [Appendix 3](#), and [Appendix 4](#)). At the Week 120 visit for patients switching to PDP OCR treatment, mandatory MRI scans should be obtained within 4 weeks before the Week 120 visit.

The mandatory MRI sequences are comprised of both brain and axial cervical spinal sequences if site technology is available, and data from these scans will contribute measurements for the key MRI secondary endpoints as well as novel exploratory

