1.2.2 Independent Review Facility

MRI scans will be read by a centralized reading center for efficacy endpoints. The centralized reading center will be blinded to treatment assignment, and the reading will be performed in the absence of clinical information.

Further details on scanning acquisition sequences, methods, handling and transmission of the scans, certification of site MRI radiologist/technicians, and the procedures for the blinded analysis of the scans at the central reading center are described separately in the MRI Acquisition and Procedures Manual and the Imaging Review Charter.

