4. STATISTICAL ANALYSES

4.1 GENERAL CONSIDERATIONS

As per the EMA guideline on multiplicity issues in clinical trials (EMA, 2017) and the FDA guidance for industry on multiple endpoints in clinical trials (FDA, 2022) multiple primary endpoints are designated as co-primary endpoints if study success is defined by a positive outcome in all primary endpoints.

In this SAP, the terminology co-primary endpoint and co-primary estimand is used although study success is defined by a positive outcome in at least one of the two co-primary endpoints, analogous to multiple primary endpoints.

For all continuous variables for which descriptive statistics are reported, the following will be reported: the number of observations, the mean, median, standard deviation, and minimum and maximum. The 25th and 75th percentiles (Q1 and Q3) will also be reported for selected tables. Descriptive summaries of discrete data will include frequencies expressed in terms of number and percentage of patients.

All primary and secondary efficacy endpoints will be stratified by/adjusted for:

- MRI activity, defined as any T1 Gd+ lesion(s) and/or new and/or enlarging T2 lesion(s) during the screening period (yes vs. no)
- Age (≤ 55 . vs. > 55)
- EDSS score (≤ 6.5 vs. > 6.5)
- Region (two regions: European Union, United Kingdom, and Canada vs. other)

The baseline is defined as the most recent value prior to first dose administration (or up to and including the date of randomization for non-treated patients), unless specified otherwise.

The baseline MRI is defined as the most recent MRI prior to randomization.

For EDSS and 9-HPT, baseline is defined as the most recent value prior to randomization.

There will be no imputation of the baseline outcome value, with the consequence that participants missing the baseline outcome measure will not contribute to the analyses which use change from baseline of a given outcome measure as the dependent variable.

For analysis purposes, the time of treatment discontinuation will be defined as 24 weeks after the last dose prior to the date of treatment discontinuation recorded in the electronic Case Report Form (eCRF).

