4.8 CHANGES TO PROTOCOL-PLANNED ANALYSES

The endpoint Annual rate of percent change from baseline in total volume of T2 lesions was changed to the endpoint Annual rate of change from baseline in radius of total volume of T2 lesions.

The endpoint Annual rate of percent change from baseline in total non-enhancing T1 lesion volume on MRI scan of the brain was changed to the endpoint Annual rate of change from baseline in radius of total non-enhancing T1 lesion volume on MRI scan of the brain.

The rationale for not considering the percent change from baseline is that certain patients might have zero lesions at baseline, in which case the percent change from baseline would be non-estimable. Moreover, the percent change from baseline in lesion could be highly skewed due to very small baseline values and hence would not follow a normal distribution. The radius transformation is applied as the RCRM model for the analysis relies on a normality assumption.

[figure not shown]

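### Do the T2-lesion and brain-volume rate analyses go wrong by giving every change-over-time quotient the same weight?

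*SAP*

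**What the plan says.** SAP 4.3.2 models the change in the cube root of T2 lesion volume as time multiplied by a patient-specific rate. That rate contains the treatment difference β1, the covariates and a normal random effect. SAP 4.3.3 uses the same form for percent change in brain volume from Week 24. Neither section writes out a residual variance in prose. SAP 4.8 adds only that "The radius transformation is applied as the RCRM model for the analysis relies on a normality assumption".

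The draft PROC MIXED code divides the change by time and fits "RANDOM intercept / subject=USUBJID type=un". For T2 lesions, "AVAL_N is the change from baseline in the cube root of the total volume of T2 lesions divided by time at each scheduled visit". For brain volume, "AVAL_N is the percent change from Week 24 in total brain volume divided by time at each scheduled visit". There is no WEIGHT or REPEATED statement. Standard errors come from the robust sandwich estimator, only scheduled visits are used, and the code is labelled draft until validated.

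On timing, Protocol 4.5.10 says: "Postbaseline, the mandatory MRI scans will be obtained in all patients at Weeks 24, 48, and 72". Scans then follow every 48 weeks, so the last one within the 144-week phase is at Week 120. On status, SAP 4.3 says: "If both co-primary estimands are statistically significant, then the secondary endpoints will be tested with" alpha 0.05 in a fixed order, in which these two endpoints come fifth and sixth.

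**The concern.** Dividing by time turns a measurement error e into e/t. If the scan-error SD is the same at every visit, the first T2 quotient (Week 24) has 5² = 25 times the error variance of the last (Week 120). For brain volume, with times counted from Week 24, the factor is 4² = 16. Giving such quotients equal weight looks inefficient, and the prose names no residual structure that would justify it. One extra line of code, weighting by time squared, would target the same β1 under the SAP's linear mean model.

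Precision is all that would be at stake: a wider confidence interval and a less sensitive test for two alpha-controlled secondary endpoints, and the same for the exploratory MRI rates in SAP 4.4.5 that reuse the estimator.

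**Working it through.** The documents give no standard error, power or scan-error figure for these endpoints, so there is no plan figure to reproduce.

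**1. Does the code match the equation?** Write the change as Y = t(β0 + αX + β1T + u) + e. Dividing by t gives Y/t = β0 + αX + β1T + u + e/t. The random intercept for the quotient is the random slope for the change, so equation and code agree. With no WEIGHT or REPEATED statement, PROC MIXED takes the residual variance as constant on the quotient scale. The structure is therefore fixed by the code, although the prose does not say so.

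**2. Within-patient weights, complete scans.** T2 times are in the ratio 1 : 2 : 3 : 5, brain-volume times 1 : 2 : 4, in units of 24 weeks (0.46 years).
- Coded fit: 1/4 each (T2), 1/3 each (brain volume).
- Time-squared fit, w = t²/Σt²: T2 1/39, 4/39, 9/39, 25/39 = 2.6, 10.3, 23.1, 64.1%; brain volume 1/21, 4/21, 16/21 = 4.8, 19.0, 76.2%.

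**3. Precision.** Take the between-patient SD of the annual slope as 1, the one-year scan-error SD as k, and error SD growing as t^p. Let s be the variance of the reference-scan error, as a multiple of k²; that error enters every change of a patient. Var(β1) is then proportional to 1 + k²[Σw²t^(2p−2) + s(Σw/t)²]. All of k, p and s are assumptions. For T2 with p = 0, s = 0, k = 1, the coded fit gives 1 + 0.414, the weighted fit 1 + 0.121, and the ratio is 1.26.

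Variance ratio, coded over weighted (above 1 favours time-squared weights), at k = 0.25 / 0.5 / 1:

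| Error structure | T2 | Brain volume |
|---|---|---|
| Constant | 1.02 / 1.07 / 1.26 | 1.03 / 1.11 / 1.38 |
| Constant plus equal reference-scan error (s = 1) | 1.07 / 1.25 / 1.76 | 1.09 / 1.33 / 1.88 |
| SD ∝ t^0.5 | 1.00 / 1.01 / 1.04 | 1.00 / 1.01 / 1.05 |
| SD ∝ t^0.75 | 1.00 / 0.98 / 0.94 | 0.99 / 0.98 / 0.93 |
| SD ∝ t | 0.99 / 0.95 / 0.85 | 0.98 / 0.94 / 0.82 |

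With s = 0 the two fits tie at p = 0.60 (T2) and 0.59 (brain volume). Dropout of 10% a year (the sample-size assumption in SAP 2.2), with data kept as in SAP 4.1, changes little: the constant-error T2 figure at k = 1 becomes 1.28.

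**4. How much reference-scan error tips the balance?** With SD ∝ t, T2: 0.250 + 1.221s = 0.475 + 0.376s, so s = 0.27. The independent error variance at the first scan is 0.46² = 0.21 on the same scale. The reference scan must therefore supply 0.267/(0.267 + 0.212) = 56% of the error there just to reach a tie. Brain volume gives s = 0.26 and 55%.

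**5. Is the target the same?** Only if the arm difference is linear from the reference scan. If the whole effect accrues by the first scan at rate 1 and then stays flat:
- Coded fit, T2: (1 + 1/2 + 1/3 + 1/5)/4 = 0.51. Weighted fit: 11/39 = 0.28.
- Coded fit, brain volume: (1 + 1/2 + 1/4)/3 = 0.58. Weighted fit: 7/21 = 0.33.

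If the effect starts only after the first scan, each figure is one minus the above: 0.49 against 0.72, and 0.42 against 0.67.

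In the early case with constant error and k = 1, the coded z-statistic for T2 is (0.508/0.282)/√1.26 = 1.61 times the weighted one. In the delayed case it is (0.492/0.718)/√1.26 = 0.61 times.

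**The case for a change.** The strongest case for the change starts from the reference scan. Every change for a patient is taken from one baseline or Week 24 scan, so some shared error is built in, and any such error favours time-squared weights. Constant or slowly growing scan error points the same way, and the gain reaches 1.88 in variance in the table. The code is still draft, and because the two fits can give different answers, the choice should be settled before unblinding.

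Part of this stands. The shared error is real, and the prose does omit the residual structure. But its size is unknown. SAP 1.2.2 says that "the procedures for the blinded analysis of the scans at the central reading center are described separately in the MRI Acquisition and Procedures Manual" and in the Imaging Review Charter, which are separate documents. The large ratios need k = 1 together with a reference-scan error as large as the scan error itself. At k = 0.25 with independent error the ratios are 0.98 to 1.03, which is 1 to 2% in standard error.

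The possible divergence also counts against the change. A variance ratio of 1.26 improves z by only √1.26 = 1.12 under linearity, whereas an early effect would cost far more than that and a delayed effect would gain more. Protocol 5.1.1.1 reports B-cell depletion by 14 days, so an early effect cannot be ruled out. The choice is in any case already fixed before unblinding: the SAP prints it.

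**Conclusion.** The concern does not hold. Equation and code agree, the printed code determines the residual structure, and the sandwich standard error keeps the test valid under random dropout. No bias and no loss of power can be shown from the documents.

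Whether time-squared weights would help turns on how scan error grows and how much comes from the reference scan, and neither is given. Over the assumed range the variance ratio falls on both sides of 1, from 0.82 to 1.88. The alternative would put 64% (T2) or 76% (brain volume) of a fully scanned patient's weight on Week 120, and so change which part of follow-up the estimate reflects if the effect is not linear. Reasonable statisticians could prefer either.

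The one unconditional remark is that the prose leaves the residual variance to the code. That is a matter of presentation, for two endpoints that are tested confirmatorily only after both co-primary analyses and four earlier secondary tests have succeeded. These figures rest on complete scans at the protocol's visits and on the assumed k, p and s.
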